**2.2.5. Tertiary/Exploratory Estimands**

Tertiary/exploratory endpoints may be analyzed using similar estimands or analyzed in a descriptive manner without reference to an estimand. Other supporting estimands may be used for some of the primary and secondary endpoints as a means to examine the robustness of results, compare to available literature and/or be used for future study planning as needed.

**2.3. Study Design**

This is a Phase 2, parallel-group, randomized, double-blind, placebo-controlled study to evaluate the effect of ponesegromab (PF-06946860) on HRQL, physical activity, safety, and circulating biomarkers in adult participants with HF and elevated circulating GDF-15.

For the Main Cohort (Cohort A), Cohort C, and Cohort D, following the 56-day screening period to confirm eligibility, the study will include a 22-week treatment period and a 10-week follow-up period for a total study duration of 32 weeks not including the screening period.

Approximately 416 participants will be enrolled into the Main Cohort (Cohort A) and randomized to one of 3 doses of ponesegromab (100 mg [n=18], 200 mg [n=18], or 300 mg [n=190]) or to matched placebo (n=190). Approximately 195 additional participants may be enrolled into optional Cohort C and randomized in a 2:1 ratio to either 100 mg ponesegromab (n~130) or to matched placebo (n~65). The participants in optional Cohort C will allow for a more comprehensive evaluation of the safety and efficacy of the ponesegromab 100 mg dose level compared to placebo. For each of these cohorts, blinded study drug will be administered SC Q4W for a total of 6 doses during the 22 week treatment period.

Participant randomization will be stratified based on CCI

CCI

KCCQ-23 CSS: <45 or ≥45.

The primary endpoint for the study is the change from baseline at Week 22 in KCCQ-23 CSS, an HRQL PRO instrument.

[figure not shown]
Approximately 100 participants (maximum of approximately 150) who meet all eligibility criteria for Cohorts A and C, except the requirement for serum GDF-15 concentration CCI CCI pg/mL, may be enrolled into the optional Cohort D and randomized in a 1:1 ratio to

either 300 mg ponsegromab ( $n \sim 50$ ) or to matched placebo ( $n \sim 50$ ), administered SC Q4W for a total of 6 doses during the 22 week treatment period. Participant randomization in Cohort D will be stratified by KCCQ-23 CSS:  $<45$  or  $\geq 45$ . The purpose of this optional cohort is for a supportive assessment of efficacy and safety endpoints across the spectrum of GDF-15 concentrations in participants with HF.

[figure not shown]
**Open-label, PK Cohort (Cohort B):** The primary purpose of this open-label, PK cohort is to facilitate a more comprehensive assessment of PK characteristics and PK/PD relationship of ponsegromab following single and repeated SC administration in participants with HF and elevated circulating GDF-15 concentrations.

Approximately 20 participants, after confirmation of eligibility, will be randomized to one of 3 dose levels of open-label ponsegromab (100 mg [ $n=4$ ], 200 mg [ $n=8$ ], or 300 mg [ $n=8$ ]) administered SC Q4W for a total of 4 doses, with last dose at Week 12 and follow-up to Week 22.

**Figure 1. Study Design**

### 3. ENDPOINTS AND BASELINE VARIABLES: DEFINITIONS AND CONVENTIONS

For all safety endpoints, unless otherwise stated, baseline is defined as the last pre-dose measurement. For all efficacy endpoints, unless otherwise stated, baseline is defined as the last measurement on study day 1.

#### 3.1. Primary Endpoint(s)

##### 3.1.1. Change from baseline in KCCQ-23 CSS at Week 22 (Cohort A only)

The KCCQ is a self-reported 23-item questionnaire that assesses HRQL in participants with HF over the past 2 weeks. Items assess physical limitations, symptoms (frequency, severity, and recent change over time), QoL, social interference, and self-efficacy. Response options vary by question. There are 10 summary scores within KCCQ: physical limitation, symptom stability, symptom frequency, symptom burden, total symptom score (TSS), self-efficacy, quality of life, social limitation, overall summary score (OSS), and clinical summary score (CSS). Raw summary scores are transformed to a 0-100 scale where higher scores indicate better health. The KCCQ-23 questionnaire and full scoring instructions are provided in Appendix 1.

The change from baseline in KCCQ-23 CSS will be calculated for all post-baseline timepoints.

### 3.2. Secondary Endpoint(s)

#### 3.2.1. Change from baseline in KCCQ-23 CSS, OSS, TSS, and physical limitation at Week 22 (Cohorts A and C)

See Section 3.1.1.

The change from baseline in KCCQ-23 CSS, OSS, TSS and physical limitation will be calculated for all post-baseline timepoints.

#### 3.2.2. Responses as defined by a $\geq 5$ -point increase from baseline in KCCQ-23 CSS, OSS, TSS, and physical limitation at Week 22 (Cohorts A and C)

See Section 3.1.1.

Each of these endpoints will have two levels: 'Response' and 'Non-response'. The former will be based on participants having a  $\geq 5$ -point increase from baseline in KCCQ-23 CSS, OSS, TSS, or physical limitation, respectively, at Week 22. Otherwise, participants will be classed as having a 'Non-response'. Participants with an intercurrent event of premature discontinuation of IP, prohibited procedure or inadequate compliance prior to Week 22 will have their Week 22 value censored (if not missing). Missing or censored values at Week 22 will be imputed as described in Section 5.3. Participants who die during the study will be classed as having a 'Non-response' after imputation.

These endpoints will be calculated similarly for all other post-baseline timepoints.

#### 3.2.3. Change from baseline in 6MWD at Week 22 (Cohorts A and C)

*The 6MWT is a submaximal exercise test that entails measurement of distance walked over a span of 6 minutes. The 6MWD (distance traveled in meters) provides a measure for integrated global response of multiple cardiopulmonary and musculoskeletal systems involved in exercise.*

The change from baseline in 6MWD will be calculated for all post-baseline timepoints with a valid test result.

#### 3.2.4. Change from baseline in PROMIS Fatigue 7a at Week 22 (Cohorts A and C)

*The PROMIS Fatigue 7a is a self-reported measure that assesses a range of symptoms in the past 7 days from mild subjective feelings of tiredness to an overwhelming, debilitating, and sustained sense of exhaustion that likely decreases one's ability to execute daily activities and function normally in family or social roles.*

*The short form 7A consists of 7 items that study participants will rate from 1: "Never" to 5: "Always". A global raw score ranging from 7 to 35 is calculated and can be translated into a T-score (Mean = 50, SD = 10) using the applicable score conversion table provided in Appendix 2.*

The change from baseline in PROMIS-Fatigue T-score will be calculated for all post-baseline timepoints.

### **3.2.5. Incidence of TEAEs, TESAEs, abnormal laboratory results, and vital signs (All Cohorts [A, B, C and D])**

#### **3.2.5.1. Adverse Events**

An adverse event is considered a Treatment-Emergent Adverse Event (TEAE) if the event started during the effective duration of treatment. All events that start on or after the first dosing day and time/start time, if collected, but before the last dose plus the lag time will be flagged as TEAEs. The lag time is defined by the Pfizer standard of 365 days post last dose of IP. The algorithm will not consider any events that started prior to the first dose date.

A Treatment-Emergent Serious Adverse Event (TESAE) is a TEAE which also meets the definition of a Serious Adverse Event (SAE).

A 3-tier approach will be used to summarize TEAEs. Under this approach, TEAEs are classified into 1 of 3 tiers: -

Tier 1 events: These are prespecified events of clinical importance and are maintained in a list in the product's Safety Review Plan (or similar, e.g. Safety Surveillance Review Plan).

Tier 2 events: These are events that are not tier 1 but are "common." A Medical Dictionary for Regulatory Activities (MedDRA) preferred term (PT) is defined as a Tier 2 event if there are at least 5% of participants reporting the event in either the placebo group or combined over the ponssegromab treatment groups.

Tier 3 events: These are events that are neither Tier 1 nor Tier 2 events.

Potential immunogenic AEs including potential cases of angioedema, anaphylaxis, hypersensitivity, delayed hypersensitivity reactions and events potentially meeting the Sampson criteria (as defined in Appendix 3) will be medically evaluated in a blinded manner throughout the study to determine whether or not they are immune reactions and possibly related to study drug and categorized as per guidance as: 1) Hypersensitivity, 2) Anaphylaxis, 3) Angioedema, 4) Delayed immune response and / or 5) Cytokine Release syndrome.

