8.4.1. Time Period and Frequency for Collecting AE and SAE Information

The time period for actively eliciting and collecting AEs and SAEs ("active collection period") for each participant begins from the time the participant provides informed consent, which is obtained before undergoing any study-related procedure and/or receiving study intervention, through and including the time of the final planned follow-up visit, except as indicated below, after the last administration of the study intervention.

Follow-up by the investigator continues throughout the active collection period and until the AE or SAE or its sequelae resolve or stabilize at a level acceptable to the investigator.

When a clinically important AE remains ongoing at the end of the active collection period, follow-up by the investigator continues until the AE or SAE or its sequelae resolve or stabilize at a level acceptable to the investigator and Pfizer concurs with that assessment.

For participants who are screen failures, the active collection period ends when screen failure status is determined.

If the participant withdraws from the study and also withdraws consent for the collection of future information, the active collection period ends when consent is withdrawn.

If a participant permanently discontinues or temporarily discontinues study intervention because of an AE or SAE, the AE or SAE must be recorded on the CRF and the SAE reported using the CT SAE Report Form.

Investigators are not obligated to actively seek information on AEs or SAEs after the participant has concluded study participation. However, if the investigator learns of any SAE, including a death, at any time after a participant has completed the study, and they consider the event to be reasonably related to the study intervention, the investigator must promptly report the SAE to Pfizer using the CT SAE Report Form.

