10.3.1. Definition of AE

AE Definition

 • An AE is any untoward medical occurrence in a patient or clinical study participant, temporally associated with the use of study intervention, whether or not considered related to the study intervention. • Note: An AE can therefore be any unfavorable and unintended sign (including an abnormal laboratory finding), symptom, or disease (new or exacerbated) temporally associated with the use of study intervention.

Events Meeting the AE Definition

 • Any abnormal laboratory test results (hematology, clinical chemistry, or urinalysis) or other safety assessments (eg, ECG, radiological scans, vital sign measurements), including those that worsen from baseline, considered clinically significant in the medical and scientific judgment of the investigator. Any abnormal laboratory test results that meet any of the conditions below must be recorded as an AE: 
 • Is associated with accompanying symptoms. • Requires additional diagnostic testing or medical/surgical intervention. • Leads to a change in study dosing (outside of any protocol-specified dose adjustments) or discontinuation from the study, significant additional concomitant drug treatment, or other therapy. • Exacerbation of a chronic or intermittent preexisting condition, including an increase in either frequency and/or intensity of the condition. • New condition detected or diagnosed after study intervention administration, even though it may have been present before the start of the study. • Signs, symptoms, or the clinical sequelae of a suspected drug-drug interaction. • Signs, symptoms, or the clinical sequelae of a suspected overdose of either study intervention or a concomitant medication. Overdose per se will not be reported as an AE or SAE unless it is an intentional overdose taken with possible

090177e1a1369fca\Approved\Approved On: 20-Jul-2024 06:57 (GMT)

suicidal/self-harming intent. Such overdoses should be reported regardless of sequelae.

Events **NOT** Meeting the AE Definition

- Any clinically significant abnormal laboratory findings or other abnormal safety assessments that are associated with the underlying disease, unless judged by the investigator to be more severe than expected for the participant's condition.

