- The investigator will then record all relevant AE or SAE information in the CRF.
- It is **not** acceptable for the investigator to send photocopies of the participant's medical records to Pfizer Safety in lieu of completion of the CT SAE Report Form/AE or SAE CRF page.
- There may be instances when copies of medical records for certain cases are requested by Pfizer Safety. In this case, all participant identifiers, with the exception of the participant number, will be redacted on the copies of the medical records before submission to Pfizer Safety.
- The investigator will attempt to establish a diagnosis of the event based on signs, symptoms, and/or other clinical information. Whenever possible, the diagnosis (not the individual signs/symptoms) will be documented as the AE or SAE.

Assessment of Intensity

The investigator will make an assessment of intensity for each AE and SAE reported during the study and assign it to 1 of the following categories:

- **Mild:** A type of AE that is usually transient and may require only minimal treatment or therapeutic intervention. The event does not generally interfere with usual ADL.
- **Moderate:** A type of AE that is usually alleviated with additional specific therapeutic intervention. The event interferes with usual ADL, causing discomfort, but poses no significant or permanent risk of harm to the research participant.
- **Severe:** A type of AE that interrupts usual ADL, or significantly affects clinical status, or may require intensive therapeutic intervention.

If required on the AE page of the CRF, the investigator will use the adjectives MILD, MODERATE, SEVERE, or VERY SEVERE to describe the maximum intensity of the AE. The severity of the AE should be determined using the Toxicity Grading Scale:

MILD	Does not interfere with participant's usual function.
MODERATE	Interferes to some extent with participant's usual function.

SEVERE	Interferes significantly with participant's usual function.
VERY SEVERE	Unacceptable and intolerable events or events which are irreversible or cause the participant to be in imminent danger of death.

An event is defined as "serious" when it meets at least 1 of the predefined outcomes as described in the definition of an SAE, NOT when it is rated as severe.

Assessment of Causality

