- If a participant dies during participation in the study or during a recognized follow-up period, the investigator will provide Pfizer Safety with a copy of any postmortem findings, including histopathology.
- New or updated information will be recorded in the originally submitted documents.
- The investigator will submit any updated SAE data to the sponsor within 24 hours of receipt of the information.

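### The treatment-emergent flag uses onset date alone, so a screening-onset adverse event that worsens or becomes serious on treatment may be left out of the TEAE and TESAE tables, depending on how the site records it

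*SAP*

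**What the plan says.** SAP 3.2.5.1 flags as a TEAE "All events that start on or after the first dosing day and time/start time, if collected", up to the last dose plus a lag of 365 days. It then closes the other end: "The algorithm will not consider any events that started prior to the first dose date". A TESAE is defined in the same section as a TEAE that is also serious, so it inherits the onset rule.

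Adverse events are collected well before dosing. Under Protocol 8.4.1 the active collection period "begins from the time the participant provides informed consent". Screening for Cohorts A, C and D can last 56 days (Protocol 4.1), and Protocol 8.4.1.2 has every event in the collection period entered on the CRF.

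On recording, Protocol 10.3.3 uses graded adjectives, where the CRF page requires them, "to describe the maximum intensity of the AE". Its follow-up part adds: "New or updated information will be recorded in the originally submitted documents". Protocol 10.3.1 lists among the events that meet the AE definition: "Exacerbation of a chronic or intermittent preexisting condition, including an increase in either frequency and/or intensity of the condition".

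**The concern.** A treatment-emergent definition is meant to capture what appears or gets worse on treatment. This one captures only what appears. An event that is mild in screening and severe or serious at Week 8 is on-treatment harm by any ordinary reading, yet as a single record it cannot be flagged.

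Incidence of TEAEs and TESAEs is a secondary safety endpoint in all four cohorts. The flag feeds the incidence and severity tables and, outside Cohort B, the Tier 1 and Tier 2 presentations with their risk differences (SAP 6.2.5.1). Interim safety outputs refer to the same section (SAP 7.2.1.2).

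Other safety data in the SAP are read against the participant's starting point: laboratory results take account of whether the baseline value was in range, vital signs are analysed as change from baseline, and a sufficient titer rise from a positive baseline counts as an ADA response (SAP 3.2.5.2, 3.2.5.3, Appendix 6). Adverse events have no equivalent rule.

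**Working it through.** The plan states no figure to reproduce, so the first step is to put one clinical course through the rules in two ways.

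Course: an adverse event starts mild after consent and before Day 1, is still present at first dose, and becomes severe or serious during treatment.

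- **One continuing record.** The start date stays before the first dose, and the intensity field holds the maximum. SAP 3.2.5.1 excludes it: not a TEAE, hence not a TESAE.
- **New record at worsening.** Protocol 10.3.1 accepts an exacerbation as an AE. Its start date is after the first dose, so it is a TEAE, and a TESAE if serious.

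The same course is counted in one case and not in the other. Which one applies is not stated. Protocol 8.4.3 has each event followed until it resolves or stabilises, and Protocol 10.3.3 speaks of a maximum intensity and of updating the existing documents. These lean towards one continuing record. Nothing in either document tells sites to open a new one on worsening.

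**Size, for illustration only.** Safety is reported for Cohorts A and C combined (SAP 5.2). Planned numbers from Protocol 4.1:

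- placebo: 190 + 65 = 255
- ponsegromab, all doses: 18 + 18 + 190 + 130 = 356

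Assume that 0.5% to 5% of participants have such an event kept under its pre-dose start date. This range is an assumption, not a figure from the documents.

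- placebo: 255 × 0.005 = 1.3 to 255 × 0.05 = 12.8 participants
- ponsegromab: 356 × 0.005 = 1.8 to 356 × 0.05 = 17.8 participants

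A participant who also has another TEAE still appears in the any-TEAE row, so these are upper limits for that row.

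**Effect on the comparison.** Let p1 and p0 be the true proportions with the event emerging or worsening on treatment, and u1 and u0 the proportions left uncounted because of the rule.

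Reported difference = (p1 − u1) − (p0 − u0) = (p1 − p0) − (u1 − u0)

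If u1 = u0, the risk difference is unchanged and only the incidences are low. At the opposite ends of the assumed range, u1 = 5% and u0 = 0.5%, the reported excess is 5 − 0.5 = 4.5 percentage points too small. With the values swapped it is 4.5 points too large.

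**The case against.** The strongest reply is that nothing need be lost. The protocol makes an exacerbation an AE in its own right, and if every site records it so, the onset rule works as intended. The convention may be settled in the CRF Completion Requirements (Protocol 10.1.7), which are not available here. The two recording sentences are not decisive: the intensity line applies only where the CRF asks for it, and the line on updates sits among follow-up bullets that largely concern SAE reporting. The protocol offers no competing TEAE definition, so there is no contradiction between the documents. All of this stands, and it is why the point is about what may be missed.

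A reader might go further in four ways that the documents do not support.

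- **That a screening-onset event can never be treatment-emergent.** A worsening entered as a new record is flagged.
- **That the rule hides harm in this trial.** All SAEs from consent onward go to the sponsor's safety group (Protocol 8.4.1.1). Laboratory analyses and the adjudicated deaths, HF hospitalizations and urgent HF visits do not use the flag.
- **That ordinary heart-failure symptoms are the main case.** Protocol 10.3.1 keeps expected signs and symptoms of the disease out of AE records unless they are more severe than expected. A symptom that first exceeds expectation on treatment would then have a post-dose onset and be counted.
- **That the illustrative percentages can be set against the Tier 2 reporting threshold.** That threshold applies to each preferred term; the illustration covers any such event.

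What remains is that the SAP states an explicit exclusion, and no visible text ensures that sites record events in the way that would make it harmless.

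**Conclusion.** The concern holds in a limited form. As written, SAP 3.2.5.1 leaves out of the TEAE and TESAE tables any screening-onset event that worsens or becomes serious on treatment under its existing record, and counts the same course when it is entered afresh. The tables may be undercounted by an amount that cannot be derived from the documents: zero if every worsening is a new record, and about 1 to 13 placebo and 2 to 18 ponsegromab participants in Cohorts A and C under the assumed 0.5% to 5%.

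The rule is the same in every arm. It biases a between-arm difference only if worsening of this kind differs by treatment, but that is one of the things the tables should be able to show. The problem is confined to outputs built on the flag. It should be corrected, because endpoint counts should not depend on site recording habits.

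**What to change.** Replace the exclusion sentence in SAP 3.2.5.1 with a rule such as: an event that started before the first dose is also a TEAE, and a TESAE if serious, when on or after the first dose and within the lag time its intensity increases or it first meets a seriousness criterion; it is counted at the date and grade of that change.

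Pair it with one CRF completion instruction for all sites: record such a worsening as a new AE with its own start date, or enter the date of worsening in the existing record. A single convention also prevents the same worsening from being counted twice.

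The cost is one SAP sentence, a derivation and a CRF note. TEAE counts will rise slightly in all arms. There will also be some retrospective work: the data cutoff for the first interim analysis (08 October 2024) precedes this SAP version (18 October 2024), so many records already exist. Where only a maximum intensity was stored, it cannot show whether the peak came before or after the first dose, and those events will need queries.
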